Aim: The aims of this study are to determine the feasibility and acceptability of the simplified 10-step Tai-chi programme for PWD, and to explore the preliminary effects of this intervention on the motor performance of PWD.

Design: A single-blinded cluster RCT will be used to compare the experimental and the control groups. An independent, trained research assistant (RA-assessor) who is blinded to the group assignment will perform the outcome assessments and data entries. A descriptive, qualitative design with focus groups or individual interviews will be used to evaluate the process of implementing the intervention from the perspectives of the participants, their caregivers, and the Tai-chi instructor.

Setting and Sampling: Four community health centres which provide services to PWD will be invited by a convenience sampling method to participate in the study. We will only recruit those community health centres that are funded by the Hong Kong (HK) government and that are under the supervision of Social Welfare Department, which meet a specific set of standardized regulations and criteria on practices, and which provide similar sets of care services for community-dwelling older people. The study's target population is community-dwelling older people with mild to moderate dementia.

The inclusion criteria for participants are: 1) community-dwelling older people of either gender; 2) who are able to communicate in Cantonese to ensure that they understand our instructions during the training, 3) who are able to walk independently with no walking aid or no more than a single point stick for at least 10 minutes so as to ensure their mobility is good enough to allow them

to take part in the Tai-chi training. 4) They must also have received a formal diagnosis of any form of dementia. Their level of cognitive impairment will be assessed using an Abbreviated Mental Test (AMT)^{28, 29} with a score ranging between 5 and 8 to indicate mild to moderate cognitive impairment. 5) Finally, they must identify a caregiver who is willing to work as an exercise partner and facilitator for their practice of Tai-chi.

Sample size: Thirty participants will be recruited for each group. A small sample of 30 per group would be sufficient to test the feasibility of a pilot study³⁰. Twenty participants from the experimental group will be randomly selected to join the focus groups after completing the entire programme.

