Sample recruitment procedures: The centres will be randomized into the control or the Tai-chi groups by using computer-generated random numbers for each of the four centres generated by an independent statistician. We will publicize/promote this study by displaying posters in the centres and asking the centre-in-charges to encourage and refer the eligible subjects to participate. A leaflet containing information about the study and an invitation letter with a reply slip for the participants to indicate their interest in participating in the study will also be mailed to all potential subjects to invite them to participate in this study. A convenience sampling method will be used to recruit participants in the community health centres.

The Interventions

The experimental condition: A 16-week 10-step simplified Tai-chi group training programme will be arranged for the Tai-chi group. During the intervention period, the participants in the Tai-chi group will receive two 1-hour centre-based Tai-chi group training sessions every week.

The participants will be required to pair up with their caregiver to take part in the training sessions together. They will be encouraged to practice the Tai-chi exercises at home for 30 minutes for at least three times per week. Adding up all of the group sessions and the time spent practising at home, each participant should have undergone at least 56 hours of Tai-chi practice during the intervention period. A high dose of 50 hours of exercise practice has been shown to be more effective in reducing fall rates than exercise interventions that require less than 50 hours of practice³¹. A maximum of 7-8 pairs of participants and their caregivers will be supervised by a qualified Tai-chi instructor during each training session. To encourage the participants to practise the Tai-chi exercises at home, a compact disc and a pamphlet describing the 10-step Tai-chi programme will be distributed.

The control condition: As no active fall prevention treatments have been employed among local older people with dementia, the control group will only take part in group recreational activities organized by the district centres. The number and timing of the activities will be similar to those organized in the Tai-chi training session for the experimental group. The participants in the control group will be also instructed to continue their usual lifestyles and levels of physical activity.

Instruments and Measures

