- Dynamic single leg standing balance will be assessed by the Step Test (ST) test³⁸. Participants will stand with their feet parallel and apart for about 10 cm. A block / step with 7.5 cm height will be placed 5 cm in front of the participants. They will be instructed to place the whole foot onto the block, then return it fully back down to the floor repeatedly as fast as possible for 15 seconds. Each leg will be tested separately, and performance on the left or right side with the least number of steps will be the result.

The number of falls will be also recorded by the caregivers and the participants in a monthly falls calendar, in which they will note down any fall accidents that have happened to the participant during the 16-week study period. Monthly phone calls will be made by an RA-observer to remind the participants to return the calendar as well as to verify the records. A fall will be defined as “an unexpected event in which participants come to rest on the floor or lower level⁴¹.” This will be used to guide the participants (caregivers) in recording their fall accidents. The severity of the injuries will also be recorded.

Procedures (randomization, allocation concealment, blinding)

After ethical approval has been obtained, all potential participants will be screened for their eligibility to participate in the study. The participants and their caregivers will then be interviewed to obtain their proxy informed consent, socio-demographic data, and baseline assessment. After that, the four community centres will be randomized to the control or the experimental groups. The participants from each centre will be placed into their centre’s corresponding group to avoid ‘contaminating’ other participants. The changes in the above mentioned preliminary outcome scores from the baseline to interim assessment at Week 8 (T1:Mid-term of intervention) and intervention effects at immediate (T2) after completion of the 16-week interventions will be compared between the groups by the RA-observer.

Twenty participants from the Tai-chi group will be randomly selected to join the focus groups within two weeks after completing the entire programme. Each focus group will contain between 5 and 10 people. The Tai-chi instructor will also be interviewed individually. All interviews will be conducted by the PI in the community health centres to collect the opinions on the design of the intervention. (Appendix II: Timeline of the study)

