All workshops and Tai-chi sessions must follow the protocols and will be run by the same RA/Tai-chi instructor to ensure intervention consistency. Intervention fidelity checking will be conducted in the training period and then monthly to bimonthly during the intervention period based on the workshop/ Tai-chi checklists. Achieving a fidelity rate of >90% will be considered acceptable, based on the recommendations of the NIH Behaviour Change Consortium⁴². This is to ensure that all of the interventions are executed by the Tai-chi instructor or the RA as intended. Monthly to bi-monthly quality-control meetings with all research personnel (the Tai-chi instructor and the RA) will be arranged to evaluate their instruction / facilitation skills in this study.

Statistical Analysis

SPSS will be used for data analysis. Descriptive statistics will be generated for the demographic data. Normality assumptions for the variables will be checked. The paired t-test or Wilcoxon's signed rank test will be used to examine any significant difference in outcome measurements in the experimental group before and after the implementation of the combined intervention. Student's T-test or the Mann-Whitney U test will be used to examine any significant differences between the control and experimental groups in terms of the outcome variables. For categorical and dichotomous outcome variables, a χ^2 test will be used to identify any significant differences between the groups. A p-value < 0.05 will be considered statistically significant. Mixed effect modelling (MEM) will be further used to measure changes in the outcome measures after intervention with respect to its baseline, and to see the effectiveness of the intervention. Multiple imputations will be adopted to manage missing data.

All interviews will be transcribed and analyzed by content analysis so as to understand participants', caregivers' and the Tai-chi instructor's opinions about the intervention. ???Coding will occur independently by two members of the research team. Differences in coding between the independent coders will be resolved through discussion between the coders.

Ethical Consideration

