Official Title: The Effects of Simplified 10-step Tai-chi Programme
on the Motor Performance and Fall Prevention of Community-
dwelling Older People With Dementia: a Pilot Cluster Randomized
Control Trial

Date of the document: 16 May 2016

**The effects of a simplified 10-step Tai-chi programme on the motor performance and fall prevention of community-dwelling older people with dementia (PWD):
A pilot cluster RCT study**

Statistical Analysis

SPSS will be used for data analysis. Descriptive statistics will be generated for the demographic data. Normality assumptions for the variables will be checked. The paired t-test or Wilcoxon's signed rank test will be used to examine any significant difference in outcome measurements in the experimental group before and after the implementation of the combined intervention. Student's T-test or the Mann-Whitney U test will be used to examine any significant differences between the control and experimental groups in terms of the outcome variables. For categorical and dichotomous outcome variables, a χ^2 test will be used to identify any significant differences between the groups. A p-value < 0.05 will be considered statistically significant. Mixed effect modelling (MEM) will be further used to measure changes in the outcome measures after intervention with respect to its baseline, and to see the effectiveness of the intervention. Multiple imputations will be adopted to manage missing data.

All interviews will be transcribed and analyzed by content analysis so as to understand participants', caregivers' and the Tai-chi instructor's opinions about the intervention. Coding will occur independently by two members of the research team. Differences in coding between the independent coders will be resolved through discussion between the coders

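### Four centres are randomised, but the between-arm t, Mann-Whitney and chi-square tests treat 60 participants as independent, so p-values are too small if the analysed outcome is correlated within centres

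*SAP*

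**What the plan says.** The unit of randomisation is the centre. Under Procedures, the Protocol says that "the four community centres will be randomized to the control or the experimental groups", and every participant takes the arm of their centre. On sample size it says "Thirty participants will be recruited for each group", justified as enough for a feasibility pilot, with no ICC or design effect.

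The SAP (Statistical Analysis), repeated in the Protocol's section of the same name, says that Student's "T-test or the Mann-Whitney U test will be used to examine any significant differences between the control and experimental groups". For categorical and dichotomous outcomes, a chi-square "test will be used to identify any significant differences between the groups". The significance criterion is p < 0.05. Then "Mixed effect modelling (MEM) will be further used to measure changes in the outcome measures after intervention with respect to its baseline", and to judge effectiveness. Neither text mentions clustering, a centre effect, a centre-level analysis or robust standard errors.

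The Procedures section indicates what is compared: "The changes in the above mentioned preliminary outcome scores from the baseline to interim assessment at Week 8", and likewise the effects immediately after the 16-week programme (T2).

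**The concern.** The three two-group tests assume independent observations. Participants in one centre share an allocation, a setting and group sessions. The Protocol makes centre differences in change plausible. For controls, "the control group will only take part in group recreational activities organized by the district centres", and Tai-chi is taught to groups of at most 7 to 8 participant-caregiver pairs. The Protocol also recruits centres with similar services and uses one instructor. Both may lower the within-centre correlation, but neither makes it zero.

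At stake is a difference in change between two sets of centres being declared a significant Tai-chi effect on Timed-up-and-Go, chair stand, functional reach or step test, or on any dichotomous outcome tested by chi-square. Such a signal could then be carried into the main study that the Protocol foresees.

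**Working it through.** **Inputs from the documents:** 4 centres; 30 participants per arm; criterion p < 0.05.

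**Assumptions, because the documents are silent:** two centres per arm, 15 participants per centre, two-sided tests, no dropout, a 30% event rate for chi-square, and a range of ICCs. The ICC is always that of the quantity analysed.

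**Step 1. The plan's own 5% level.** At ICC 0 the simulated rejection rates under no effect are 0.049 (t), 0.047 (Mann-Whitney) and 0.048 (chi-square). The nominal level is reproduced when there is no clustering.

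**Step 2. With clustering.** Design effect = 1 + (15 − 1) × ICC. Approximate true level = 2 × [1 − Φ(1.96 / √design effect)]. At ICC 0.05 the design effect is 1 + 14 × 0.05 = 1.70, so 60 participants carry the information of 60 / 1.70 = 35.3. Simulated rates use 200,000 null trials per ICC (40,000 for Mann-Whitney):

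| ICC | Design effect | Approx. level | t-test | Mann-Whitney | Chi-square |
|---|---|---|---|---|---|
| 0.01 | 1.14 | 0.066 | 0.067 | 0.063 | 0.065 |
| 0.02 | 1.28 | 0.083 | 0.083 | 0.081 | 0.083 |
| 0.03 | 1.42 | 0.100 | 0.100 | 0.094 | 0.099 |
| 0.05 | 1.70 | 0.133 | 0.134 | 0.128 | 0.133 |
| 0.10 | 2.40 | 0.206 | 0.212 | 0.200 | 0.213 |

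A t-test on the four centre means (2 df) rejects 0.050 to 0.051 in the same trials, and centre proportions 0.049 to 0.051.

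**Step 3. Change scores.** Stable centre differences cancel. Take a cross-sectional ICC of 0.05, a within-person correlation of 0.7, and a share f of centre variance that is specific to the time point (all assumed). Then

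ICC of change = 2 × 0.05 × f / [2 × 0.05 × f + 2 × 0.95 × (1 − 0.7)].

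- f = 0: ICC of change 0; the t-test rejects 0.051.
- f = 20%: 0.02 / (0.02 + 0.57) = 0.03; the t-test rejects 0.107.
- f = 50%: 0.05 / (0.05 + 0.57) = 0.08; the t-test rejects 0.186.

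Mean change per centre on 2 df rejects 0.049 to 0.052 in all three cases (20,000 runs).

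**Step 4. Does the mixed model rescue the plan?** In a model of baseline, T1 and T2 with no centre-by-time term, the arm-by-T2 contrast judged against a normal reference rejects 0.057 / 0.113 / 0.187 for the same three values of f, almost the same as the t-test. A constant centre intercept does not help, because it drops out of that contrast. A one-time-point REML model with a random centre effect rejects 0.088 (ICC 0.05) and 0.119 (ICC 0.10) with a normal reference, but 0.001 and 0.004 with 2 df, because centre variance is estimated as zero in 43% and 31% of trials.

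**Step 5. What four centres support.**

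- Half-width of the 95% interval on 2 df at ICC 0.05: 4.303 × √(0.05 + 0.95/15) = 1.45 SD.
- Half-width from the participant-level t-test: 2.00 × √(2/30) = 0.52 SD.
- Power on 2 df at ICC 0.05: 15% for 0.5 SD and 28% for 0.8 SD.
- An exact two-sided permutation test of 2 against 2 centres cannot give p below 2/6 = 0.33.

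**The case against.** The best defence is that this is a pilot. Feasibility and acceptability come first among the aims, and the motor outcomes are there only to "explore the preliminary effects of this intervention on the motor performance of PWD". No motor outcome is primary and no progression rule depends on a p-value. The Protocol mentions a future main study only when discussing recruitment difficulties. This limits the consequences, but the SAP itself chose significance tests at 0.05 and a model to judge effectiveness. Even an exploratory p-value needs a valid standard error.

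The size is also assumed. No ICC is stated, and for change scores the inflation disappears if centre differences are stable. Below an ICC of about 0.02 it is mild. This stands: the omission is certain, its size is not. The chi-square result has the weakest footing, because no dichotomous efficacy outcome is named and the 30% event rate is illustrative.

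The mixed model could be called under-specified rather than wrong, but it is an addition and leaves the simple tests in place. The documents do not state a 2:2 split of centres, but centre means on 2 df also hold about 5% under a 1:3 split. Finally, the corrected analysis has little power. That is true, but it reflects the design and does not justify the narrower interval.

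**Conclusion.** The concern holds. Every between-arm test named in the SAP ignores the unit of randomisation, and the mixed model as described does not repair this. The plan is wrong as written, not merely brief. The true level of a nominal 5% test stays near 5% only if the ICC of the analysed outcome is close to zero. It doubles at about 0.03 and reaches about 21% at 0.10. These figures rest on the assumptions listed in the working, chiefly the ICC range and the equal 2:2 split. Feasibility measures are largely unaffected, so the fault lies in the between-arm claims. It should be corrected before any between-arm analysis is run.

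**What to change.** In both the SAP and the Protocol, replace the participant-level between-arm tests with wording such as:

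> Arms will be compared at T1 and T2 using one summary per centre (mean change from baseline, or proportion), as a difference with a 95% confidence interval from t on 2 df. P-values are exploratory. The ICC of change will be reported with its interval.

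- State the number of centres per arm, since 2:2 is only assumed here.
- If baseline adjustment is wanted, estimate the slope from participants within centres and then average by centre, so that no centre-level degree of freedom is spent. This rejected 0.046 to 0.054 under no effect (8,000 runs, ICC 0.05 and 0.10).
- Do not use a centre-level rank or permutation test, given its floor of 0.33 with 2 against 2 centres.
- If the mixed model is kept, give it a centre-by-time effect, or a centre effect in a baseline-adjusted model at each time point, with degrees of freedom based on four centres. Label it supportive. The unadjusted one-time-point version almost never rejects on 2 df, and the centre-by-time version was not simulated.
- Say how centre summaries will be formed from the multiply imputed data.

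The change costs wording only and needs no new data. The real price is precision, as step 5 of the working shows, and the plan should say so. The motor results should be read as estimates, and the ICC interval will be wide as well.

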Social-demographic data (age, gender, marital status, exercise habits, living conditions, and level of education) will be collected. The participants' health-related information will also be collected, including their morbidities, cognitive status, fall history, and medications taken in the past 12 months.

The feasibility assessment includes the ease of recruitment, the acceptance rate, the dropout rate, the engagement of PWD when attending the Tai-chi training sessions, the adherence to practising Tai-chi at home and at training sessions, the occurrence of adverse events, and feedback from the participants (caregivers) as well as the Tai-chi instructor.

- **Ease of recruitment** – if any difficulties encounter during the recruitment phase will be recorded to consider for improvements in the future main study.
- **Acceptance rate** refers to the proportion of subjects who provide proxy consent to join the study over the eligible participants will be calculated for the acceptance rate.

- Dropout rate – percentage of participants withdrawing from the study will be recorded and the reasons for withdrawal will be asked
- Engagement of participants when attending the Tai-chi training sessions will be assessed by the Non-pharmacological Therapy- Experience Scale (NPT-ES). This scale was developed by Muñiz et al in 2011 with an aim to measure the immediate emotional and social effects of any kind of non-pharmacological interventions delivered to PWD³³. It is a 5-item scale which includes participation, pleasure, relationship with others, displeasure and rejection (the last two are reverse items). Each item is rated on a 4-point scale from 0 =Never to 3= Always. By summing up all five item scores to get the total score ranged from zero to fifteen, higher scores indicating more positive experience. All Tai-chi training sessions will be video-taped. The well-trained research assistant (RA) will assess the engagement of each participant during each training session based on both real time and the video observations. The Tai-chi instructor will also be required to comment on the engagement of each participant in terms of whether or not a particular participant can follow each Tai-chi step appropriately based on her observations during the training sessions.

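### Falls are a 16-week calendar count with no assigned analysis, and the SAP's listed group comparisons would ignore follow-up time: a minor, cheap improvement

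*SAP*

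**What the plan says.** The Protocol, at the end of the preliminary outcomes part of Instruments and Measures, states: "The number of falls will be also recorded by the caregivers and the participants in a monthly falls calendar". The period is the 16-week study, a fall is defined, and the calendars are chased: "Monthly phone calls will be made by an RA-observer to remind the participants to return the calendar as well as to verify the records".

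The SAP, whose statistical text matches the Protocol's Statistical Analysis section, does not mention falls. For group comparisons of outcomes in general it gives Student's t-test, with this alternative: "the Mann-Whitney U test will be used to examine any significant differences between the control and experimental groups in terms of the outcome variables". It gives a chi-square test for categorical outcomes. It adds: "Mixed effect modelling (MEM) will be further used to measure changes in the outcome measures after intervention with respect to its baseline". On incomplete data it has one sentence: "Multiple imputations will be adopted to manage missing data".

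On withdrawal, the Protocol's feasibility list says: "percentage of participants withdrawing from the study will be recorded and the reasons for withdrawal will be asked". It does not list a withdrawal date or the last calendar returned. The effect part of the Aim is "to explore the preliminary effects of this intervention on the motor performance of PWD"; falls appear in the title but not in the Aim. On clusters: "Four community health centres which provide services to PWD will be invited by a convenience sampling method".

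**The concern.** A calendar count grows with the time observed. A participant who leaves at week 8 has had half the opportunity to record a fall. None of the listed methods carries a term for that time, so if one of them is used on the raw count, an arm that loses more people looks as if it falls less.

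The imputation sentence does not settle this. A partial count is an observed number unless someone codes it as missing. The plan does not say whether the returned calendars stand as they are, are discarded with the participant, or are completed by imputing the remaining months. These choices can give different answers from the same data.

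Two things are at stake: the fall ratio between arms, and the fall rate itself. The Protocol foresees a later main study. It does not say that this pilot's fall rate will be used to plan it, but that would be a natural use.

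**Working it through.** There is no plan figure to reproduce. The 30 per group rests on a general reference for pilot studies, with no fall rate, effect size or power.

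**Inputs from the documents.** 30 per arm; four centres; 16 weeks. The only completion figure is 86.4%, from a 16-week Tai-chi programme cited in the Protocol's background, so 100 - 86.4 = 13.6% non-completion.

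**Assumptions.** No true effect; mean m = 0.3, 0.6 or 1.0 falls per 16 weeks; negative binomial falls with dispersion 1; the withdrawal splits shown. Ratios are the arm with the first-named withdrawal share over the other arm.

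**Case A: leaving is unrelated to falls and happens half-way on average.** With withdrawal share d, mean follow-up is 1 - 0.5d. The ratio of raw mean counts is (1 - 0.5·d1)/(1 - 0.5·d2).
- 13.6% v 0%: 0.932/1 = 0.93
- 30% v 0%: 0.85/1 = 0.85
- 10% v 30%: 0.95/0.85 = 1.12
- equal shares: 1.00

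With equal shares, raw falls per participant still understate the 16-week rate by 0.5d: 7% at 13.6% and 15% at 30%.

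Against sampling error at m = 0.6, the standard error of the log ratio is sqrt((1/0.6 + 1)·(2/30)) = 0.422. Since -ln(0.932) = 0.070, the shift is 0.070/0.422 = 0.17 standard errors.

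**Case B (extreme): all leaving follows a fall, in one arm only.** Let each fall trigger leaving with probability p. With dispersion 1 the share completing is 1/(1 + p·m). Setting this to 0.864 gives p·m = 1/0.864 - 1 = 0.157, so p = 0.525, 0.262 and 0.157 at m = 0.3, 0.6 and 1.0.
- *Partial counts kept.* Leavers = p × falls observed, so falls observed = 0.136/p = 0.864·m. Ratio 0.86 at every m.
- *Withdrawers dropped.* Completers' mean is m·(1 - p)·0.864. The ratio (1 - p)·0.864 is 0.41, 0.64 and 0.73.
- *Falls per person-time.* Mean follow-up is ln(1.157)/0.157 = 0.929. Ratio 0.864/0.929 = 0.93.

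Simulation with at least 600,000 per arm agrees with these three results. It also gives 1.00 for imputation that uses each withdrawer's observed falls and time (true parameters, so a best case). A negative binomial model with a follow-up offset gives 1.00 if the last part-filled calendar is obtained, but 0.44, 0.68 and 0.78 if it is lost.

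**False positives in case A** (Mann-Whitney on raw counts, 30 per arm, 6,000 runs, no centre effect; at m = 0.3, 0.6, 1.0):

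| Withdrawal | Rejections |
|---|---|
| 13.6% v 0% | 5.2%, 4.8%, 5.5% |
| 30% v 0% | 6.0%, 6.4%, 7.5% |
| 40% v 10%, all at week 4 | 7.4%, 9.6%, 11.8% |

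The t-test at 13.6% v 0% gives 5.0%, 5.0% and 5.1%.

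**The case against.** The other side has a good deal on its side.

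- A reader might infer that the SAP has chosen the Mann-Whitney test for falls. It has not: it assigns no test to falls, and descriptive reporting is an equally open reading. The point is therefore conditional on a listed method being used.
- A reader might infer that withdrawers will be dropped, so that 0.41 to 0.73 is the expected bias. The only stated rule is multiple imputation, and imputation that uses the observed falls and time recovers 1.00. In case A, dropping withdrawers is also unbiased. The low figures need both fall-driven leaving and loss of the observed falls. Imputing 16-week totals without those falls should come close to the same result.
- The 13.6% is non-completion of a cited programme. It is not loss of fall follow-up, and it says nothing about a difference between arms. The control arm is offered activities of similar number and timing, so 0% loss there is purely an assumption.
- A reader might infer that withdrawal dates will not be kept. The feasibility list defines a dropout percentage and is not a form specification. Monthly returns, verified by phone, already show much of the time covered.
- A count model is not a cure. With an assumed between-centre standard deviation of the log rate of 0.2 or 0.4 (at 0.6 falls), negative binomial false positives reach 8.2% or 13.4%. This does not favour the listed test, since Mann-Whitney reaches 7.4% and 13.3% there.

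What stands is that none of the listed group comparisons uses follow-up time, that the handling of partial calendars is open, and that a person-time rate costs almost nothing.

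**Conclusion.** The point holds as a minor improvement. If a listed method is used on the raw count, unequal withdrawal shifts the fall ratio by about 7% (13.6% v 0%) to 15% (30% v 0%) when leaving is unrelated to falls, and not at all when withdrawal is equal. Fall-driven leaving could do more, but that is an extreme assumption.

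A reader might infer that the planned tests would often declare a false effect on falls. The figures do not support this: rejection is about 5% at 13.6% v 0% and rises clearly only when withdrawal is early and very unequal. The shift of 0.17 standard errors is small beside the imprecision of 30 per arm in four centres.

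Fall rates, dispersion, withdrawal splits and the link between falling and leaving are all assumed. Falls lie outside the stated aims, which further limits the importance.

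**What to change.** 1. **Data collection.** Record the withdrawal date and the last calendar returned. Ask for the part-filled calendar at the contact where reasons for withdrawal are already sought.
2. **SAP, one paragraph.** Report falls and person-time by arm and by centre, keeping all returned calendars, including those of withdrawers. In place of a test on raw counts, give an exploratory rate ratio from a count model with log follow-up time as offset: negative binomial, or Poisson with an overdispersion-corrected variance. Plain Poisson should not be used; it rejected in 6.5%, 10.5% and 15.6% of null runs at 0.3, 0.6 and 1.0 falls (13.6% v 0%).
3. **Caveat in the SAP.** State that a participant-level interval ignores centre and is too narrow with four centres. At 0.6 falls its 95% limits are the estimate divided and multiplied by exp(1.96 × 0.422) = 2.3. With the t quantile on 2 degrees of freedom for four centres, the factor is exp(4.303 × 0.422) = 6.1, even before any between-centre variation.

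The cost is two form fields, one paragraph and slightly more analysis work. Residual bias remains if withdrawal is fall-driven and the last calendar is lost, and simple falls per person-time still gives 0.93 in case B.
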